10.8.2. Insulin Degludec

Insulin degludec will be administered at a starting dose of 10 Units. For subsequent dose adjustments, a dosing algorithm (adapted from Riddle et al. 2003) will be used by investigators

for initiating and adjusting insulin degludec to target an FG ≤ 100 mg/dL (< 5.6 mmol/L) for patients to achieve glycemic goal.

In situations where patient safety is a concern or where dose adjustments have not had the desired therapeutic effect, investigators may make increased or decreased adjustments to the dose of insulin degludec recommended by the dose-adjustment algorithm and have to document the clinical rationale for the deviation as well as inform Lilly Medical per email.

At the time of site visit or telephone visit, the investigator will assess the patient's glycemic control for the previous week and, if necessary, inform the patient about any needed dose adjustment. The dose will be based on the patient's blood glucose value. Adherence to the dosing algorithm provided for this study is mandatory from Visit 3 (randomization) up to Visit 20 (Week 26), inclusive. Dose increases may be made at weekly intervals and no sooner than 5 days following the last dose increase. In some cases, patient visits could occur sooner than 5 days apart due to the allowable visit window; however, there should be no dose increase if at least 5 days have not elapsed since the previous dose increase. In contrast, the insulin degludec dose may be reduced at any time on the judgment of the investigator. Any deviations from this guidance must be supported by clinical evidence and accompanied by information of Lilly Medical.

Insulin dose algorithms have been reviewed by Strange (2007). The insulin degludec dose increase algorithm is adapted from Riddle et al. 2003 and will be determined based on the definition of what is termed the "Algorithm FG." The Algorithm FG is the median of the FG (determined from SMBG) of Days 5, 6, and 7 since the last insulin dose increment. If the interval since the last dose adjustment has been longer than 7 days, the dose increase is determined by the median of the FG of the last 3 days. If the patient only measured their FG on 2 of the last 3 days, then the lesser of those 2 FG values should be used as the Algorithm FG. If only 1 FG measurement is available for the last 3 days, then the investigator should use his/her discretion in determining whether there should be a dose adjustment based on that single FG value.

As it is desired to achieve glycemic goals in as many patients as possible, contingencies are provided to accommodate prespecified protocol visits and to increase the dose of insulin degludec in a timely manner. Therefore, if the last dose increment was 5 days previous, then the dose increment is determined by the Algorithm FG, which is the lesser of the 2 FG values from Day 4 and Day 5. If the dose increment was 6 days previous, then the Algorithm FG is the lesser of the 2 FG values from Day 5 and Day 6. In both of these cases, if only 1 of the 2 FG values is available, then the investigator should use his/her discretion in determining whether there should be a dose adjustment based on that single FG value.

The dose increase algorithm is defined as follows:

- If the Algorithm FG is 101 to 120 mg/dL (5.6 to 6.7 mmol/L), increase the dose by 2 U
- If the Algorithm FG is 121 to 140 mg/dL (6.8 to 7.8 mmol/L), increase the dose by 4 U
- If the Algorithm FG is 141 to 180 mg/dL (7.9 to 10.0 mmol/L), increase the dose by 6 U
- If the Algorithm FG is > 180 mg/dL (10.0 mmol/L), increase the dose by 8 U

The treat-to-target FG is ≤ 100 mg/dL (< 5.6 mmol/L). The insulin degludec dose will not be increased if any SMBG was documented at ≤ 70 mg/dL (< 3.9 mmol/L) at any time in the

preceding week. Dose decreases of 2 to 4 U per adjustment may be permitted if multiple episodes of hypoglycemia with SMBG ≤ 70 mg/dL (< 3.9 mmol/L) were recorded, if severe hypoglycemia (requiring assistance) occurred, or if any SMBG was documented at ≤ 54 mg/dL (≤ 3.0 mmol/L) in the preceding week.

[figure not shown]

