4.1.1. Study Visits

Study Period 1: Screening and Lead-in

The purpose of procedures at screening is to establish eligibility for inclusion in the study (see Sections 5.1 and 5.2). During this period (upon signing the informed consent form [ICF]), study participants will be trained on disease monitoring and disease management procedures, study diaries, and study procedures. For all participants meeting study entry criteria except for reporting of screening clinical laboratory assessments, a LibrePro sensor for flash glucose monitoring (FGM) will be inserted and activated at Visit 1 for baseline FGM assessment. If the patient is ultimately determined a screen failure, the sensor can be removed and discarded or the patient can continue wearing for up to 14 days and return to the site for reading and diagnostics. All confirmed eligible participants should continue wearing the sensor for up to 14 days and to wear the sensor to Visit 3 for removal or bring the sensor with them to Visit 3 if this visit occurs longer than 14 days after insertion.

Electronic participant diaries and participant paper note sheets will be dispensed at Visit 2 and as specified in the Schedule of Activities (Section 1.3) for future visits. Collection of baseline self-monitoring blood glucose (SMBG) profiles will start at Visit 2. Participants on metformin (alone or in combination with a stable dose of a DPPIV inhibitor and/or a SGLT2 inhibitor) will continue on their same dose to allow reliable assessment of HbA1c at randomization.

If participants develop a condition that is a contraindication for the use of metformin, a DPPIV inhibitor and/or a SGLT2 inhibitor (if used at screening) or initiate other agents that are prohibited (see table in Section 6.5 and Sections 5.1 and 5.2 for further details) between screening and randomization, they will be considered ineligible and will be discontinued from the trial before randomization.

SMBG:

All patients will be provided with identical blood glucose meters for taking self-monitored plasma glucose measurements during the outpatient period at Visit 2.

Study Period 2: Treatment Period

Randomization (Week 0 [Visit 3])

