10.8. Appendix 8: Dosing Guidance for LY3209590 and Insulin Degludec

10.8.1. LY3209590 Algorithm 1 (paper algorithm)

In Study BDCL, a paper dosing Algorithm 1 will be used by investigators for initiating and adjusting LY3209590 to achieve the target FG ≤ 100 mg/dL (< 5.6 mmol/L).

In situations where study participant safety is a concern, investigators may adjust the dose of LY3209590 recommended by the dose-adjustment algorithm in Table 2; however, clinical rationale must be documented in the eCRF and Lilly Medical must be informed about this deviation and associated medical rationale. If the investigator has safety concerns about the algorithm, the investigator is to contact the Lilly CRP.

At the time of site visit, the investigator will assess the study participant's glycemic control for the previous week and, if necessary, inform the study participant about any needed dose adjustment. The dose will be based on the study participant's FG value from SMBG and hypoglycemia documented in the previous week. Adherence to the dosing algorithm provided for this study is required from Visit 3 (randomization) up to Week 25 and will be monitored periodically by the study team.

General Algorithm Considerations:

- The treat-to-target FG in the algorithm is ≤ 100 mg/dL (< 5.6 mmol/L). LY3209590 dose adjustments will be determined based on the median of the FG from SMBG of at least 3 days (up to 7 days) obtained in the previous week leading up to the visit.
- The LY3209590 dose may not be increased if any SMBG reading was documented at ≤ 70 mg/dL (< 3.9 mmol/L) at any time in the preceding week. Dose decreases of 0.5 mg adjustment may be permitted if multiple episodes of hypoglycemia with SMBG ≤ 70 mg/dL (< 3.9 mmol/L) were recorded, or dose decrease of 1 mg if severe hypoglycemia (requiring assistance) occurred, or if any SMBG was documented at ≤ 54 mg/dL (≤ 3.0 mmol/L) in the preceding week.
- In dosing calculations where rounding is required, round to the nearest 0.25 mg

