The initial (Week 0, Visit 3) LY3209590 dose is based on the baseline median fasting glucose and body weight at Visit 3. Because of the long half-life of LY3209590, the change in fasting glucose response following the initial dose may take several weeks to reach desired response; therefore, to minimize the time needed to achieve the desired target glycemic response, the initial dose was **CCI** in order to achieve steady-state concentration within the first week. Directions are provided below to determine the initial dose using Table 1 and for dose adjustments at subsequent visits using Table 2. Examples for Visits 3-6 are provided in *italic text*.

Visit 3 (Randomization Visit):

1. Determine the initial dose by obtaining the participant's body weight and median FG in the week prior to Visit 3 and consulting Table 1.

For example, if a participant weights 83 kg and has a median FG of 185 mg/dl, according to Table 1, the initial dose of LY3209590 is 10.5 mg.

Table 1. Determination of Initial Dose^a of LY3209590 at Visit 3 using Median of Baseline Fasting Glucose and Body Weight

Median Baseline Fasting Glucose (mg/dL)	Median Baseline Fasting Glucose ^b (mmol/L)	Body Weight (kg) at Visit 3			
		≤80	80.1 – 100	100.1 – 120	≥120.1
≤140	≤7.7	3 mg	4.5 mg	6 mg	7.5 mg
141 – 180	7.8 – 10.0	6 mg	7.5 mg	10.5 mg	12 mg
181 – 220	10.1 – 12.2	9 mg	10.5 mg	12 mg	13.5 mg
>220	>12.2	12 mg	13.5 mg	15 mg	16.5 mg

a The initial dose reflects the 3-fold increase needed to reduce the time to target glycemic response and should ONLY be administered once at Visit 3.

b Conversions from mg/dL to mmol/L were rounded off to prevent overlap between threshold ranges and to address that the glucose meter displays 1 significant digit after the decimal when reporting mmol/L readings.

Visit 4 (Week 1)

1. Calculate the total weekly dose LY3209590 mg from the dose administered at Visit 3. (this is **CCI** the dose administered at Visit 3)

*From the Visit 3 example, the LY3209590 total weekly dose is **CCI**.*

2. Use Table 2 to determine the dose adjustment needed for Visit 5 after carefully reviewing participant's fasting glucose (3-7 days prior to visit) and hypoglycemia documented since the last LY3209590 dose.

The participant reported no hypoglycemia since the last dose of LY3209590 and had a median FG of 175 mg/dL. Using the Week 1 (Visit 4) column, the LY3209590 weekly dose should be increased by 3 mg.

3.5 mg + 3 mg = 6.5 mg LY3209590 should be administered at Visit 4.

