Table 2. Weekly Dose Adjustment of LY3209590 using the Previous Week's dose (D), Median Fasting Glucose and Hypoglycemic Episodes

Median Fasting Glucose (mg/dL) ^a	Median Fasting Glucose (mmol/L) ^{a,e}	Week 1 (Visit 4) (2 nd dose)	Week 2 (Visit 5) (3 rd dose)	Subsequent Week ^c	
				Dose ≤5 mg	Dose >5 mg
<80 mg/dL or have any nocturnal hypoglycemia or multiple episodes of hypoglycemia ^d	<4.4 mmol/L or have any nocturnal hypoglycemia or multiple episodes of hypoglycemia ^d	D ^b – 1.5 mg	D ^b – 1.5 mg	D ^c – 1.5 mg	D ^c – 2 mg
80 – 100 mg/dL	4.4 – 5.5	D ^b – 1 mg	D ^b – 0.5 mg	No change	No change
101 – 140 mg/dL	5.6 – 7.7	No change	No change	D ^c + 0.25 mg	D ^c + 0.5 mg
141 – 180 mg/dL	7.8 – 10.0	D ^b + 3 mg	D ^b + 1.5 mg	D ^c + 0.5 mg	D ^c + 1 mg
>180 mg/dL	>10.0	D ^b + 5 mg	D ^b + 3 mg	D ^c + 0.75 mg	D ^c + 1.5 mg

- a Based on median fasting glucose from at least 3 fasting glucose from previous week.
- b D for Week 1 (Visit 4) is **CC** of the initial dose from Table 1. D for Week 2 (Visit 5) is Week 1 (Visit 4) dose.
- c LY3209590 dose adjustment starting at Week 3 (Visit 6) will depend on whether previous (Week 2) dose (D) is ≤ 5 mg or > 5 mg and will be adjusted weekly up to Week 12 (Visit 15), then at Week 16 (Visit 17), Week 20 (Visit 18), and Week 24 (Visit 19).
- d The LY3209590 dose may not be increased if any SMBG reading was documented at ≤ 70 mg/dL (< 3.9 mmol/L) at any time in the preceding week. If multiple episodes of hypoglycemia with SMBG ≤ 70 mg/dL (< 3.9 mmol/L) were recorded, follow guidance for dose reduction according to the applicable Visit number. Dose decreases of 1 mg should be made when severe hypoglycemia (requiring assistance) occurred, or if any SMBG was documented at ≤ 54 mg/dL (≤ 3.0 mmol/L) in the preceding week.
- e Conversions from mg/dL to mmol/L were rounded off to prevent overlap between threshold ranges and to address that the glucose meter displays 1 significant digit after the decimal when reporting mmol/L readings.

Visit 5 (Week 2)

1. Confirm the dose of LY3209590 mg administered at Visit 4.

From the Visit 4 example, the LY3209590 weekly dose was 6.5 mg.

2. Use Table 2 to determine the dose adjustment needed for Visit 5 after carefully reviewing participant's fasting glucose (3-7 days prior to visit) and hypoglycemia documented since the last LY3209590 dose.

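### The 140/141 mg/dL dosing edge is 7.7|7.8 mmol/L for LY3209590 but 7.8|7.9 for degludec, and on a meter that rounds to nearest the <3.9 mmol/L limit misses 70 mg/dL

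*Protocol*

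**What the plan says.** In Protocol 10.8.2 the degludec steps around the edge read "If the Algorithm FG is 121 to 140 mg/dL (6.8 to 7.8 mmol/L), increase the dose by 4 U" and "If the Algorithm FG is 141 to 180 mg/dL (7.9 to 10.0 mmol/L), increase the dose by 6 U". In Protocol 10.8.1, Table 1 pairs 140 mg/dL or less with 7.7 mmol/L or less, and Table 2 pairs 101–140 mg/dL with 5.6–7.7 mmol/L. In both tables 141–180 mg/dL is 7.8–10.0 mmol/L. So the mg/dL edge is the same in both arms and the mmol/L edge is not.

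The footnotes on conversion say that values were rounded so that ranges do not overlap, and because "the glucose meter displays 1 significant digit after the decimal when reporting mmol/L readings". Protocol 4.1.1 adds that "All patients will be provided with identical blood glucose meters for taking self-monitored plasma glucose measurements".

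For hypoglycemia, 10.8.1 says the LY3209590 "dose may not be increased if any SMBG reading was documented at ≤ 70 mg/dL (< 3.9 mmol/L"). The decrease rules use the same pairing: "if multiple episodes of hypoglycemia with SMBG ≤ 70 mg/dL (< 3.9 mmol/L) were recorded, or dose decrease of 1 mg" in the general considerations and "If multiple episodes of hypoglycemia with SMBG ≤ 70 mg/dL (< 3.9 mmol/L) were recorded, follow guidance for dose reduction" in Table 2 footnote d. The degludec hold and decrease rules in 10.8.2, the definition of documented hypoglycemia in 6.1.2.2 and the patient instructions in 8.3.7.1 repeat it. In the 10.8 rules the neighbouring 54 mg/dL limit keeps the same operator in both units (≤54 mg/dL, ≤3.0 mmol/L).

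**The concern.** These limits decide insulin doses. A site that reads mmol/L works from the mmol/L figures and should reach the same dose as a site that reads mg/dL. Where the two sets of limits disagree, a site can follow the algorithm correctly and still give a different dose, with nothing to prompt an override. With nearest rounding, the LY3209590 mismatch at 7.8 and the mismatch at 3.9 in both arms lead to more insulin. Protocol 6.7.1 says washout of LY3209590 may take up to 10 weeks, so an excess dose is slow to reverse.

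**Working it through.** **Inputs.** The limits come from Protocol 10.8.1 (Tables 1 and 2, footnote d) and 10.8.2. The one-decimal display comes from the table footnotes. The conversion factor is not stated. The rescue limits in 6.1.2.3 imply 18.0 mg/dL per mmol/L: 270/18.0 = 15.0, 240/18.0 = 13.3, 200/18.0 = 11.1. I used 18.0, 18.016 and 18.018. The documents do not say whether the meter rounds to nearest or cuts off, so both are shown.

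**Step 1: plan figures that reproduce.** 54/18.0 = 3.000 and 54/18.016 = 2.997, shown as 3.0 with rounding. 180/18.0 = 10.000 and 180/18.016 = 9.991, shown as 10.0 with rounding.

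**Step 2: values at the two limits.**

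| mg/dL | ÷18.0 | ÷18.016 | ÷18.018 | Rounded to nearest | Cut off |
|---|---|---|---|---|---|
| 70 | 3.889 | 3.885 | 3.885 | 3.9 | 3.8 |
| 71 | 3.944 | 3.941 | 3.941 | 3.9 | 3.9 |
| 140 | 7.778 | 7.771 | 7.770 | 7.8 | 7.7 |
| 141 | 7.833 | 7.826 | 7.826 | 7.8 | 7.8 |
| 142 | 7.889 | 7.882 | 7.881 | 7.9 | 7.8 |

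**Step 3: the 7.8 edge.** A displayed 7.8 goes to the higher band for LY3209590 and the lower band for degludec, while the mg/dL edge is identical. Any reading shown as 7.8 is therefore misplaced in one arm.

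- Rounded to nearest: LY3209590 misplaces 140 mg/dL (too high). Degludec misplaces 141 mg/dL (4 U instead of 6 U).
- Cut off: LY3209590 is right. Degludec misplaces 141 and 142 mg/dL, again toward the smaller step.

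**Step 4: dose at 140 mg/dL in the LY3209590 arm, nearest rounding.**

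| Decision | By mg/dL | By mmol/L (7.8) |
|---|---|---|
| First dose, ≤80 kg | 3 mg | 6 mg |
| First dose, 80.1–100 kg | 4.5 mg | 7.5 mg |
| First dose, 100.1–120 kg | 6 mg | 10.5 mg |
| First dose, ≥120.1 kg | 7.5 mg | 12 mg |
| Week 1 | no change | +3 mg |
| Week 2 | no change | +1.5 mg |
| Later, dose ≤5 mg | +0.25 mg | +0.5 mg |
| Later, dose >5 mg | +0.5 mg | +1 mg |

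Table 1 footnote a describes the first dose as a threefold increase, and SAP 5.8 takes one third of it as the baseline dose. At 80 kg or less the baseline dose is then 3/3 = 1 mg or 6/3 = 2 mg.

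**Step 5: the 70 mg/dL limit.** With nearest rounding, 70 mg/dL shows as 3.9. It meets ≤70 mg/dL but not <3.9 mmol/L, so by the mmol/L limit it does not block an increase or count toward a decrease. This is the same in both arms.

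**Step 6: how often the 140 mg/dL case could arise.** The inputs are assumptions, not plan figures: 25–50% of about 125 LY3209590 participants read mmol/L (31–63 people), and the fasting glucose used for dosing is normal with mean 110–180 and SD 25–45 mg/dL. At 18.016, a display of 7.8 starts at 7.75 × 18.016 = 139.6 mg/dL. The misplaced window is 139.6 to 140.5, with probability 0.0039 to 0.0140. Adjustments per person: Weeks 1–12, 16, 20 and 24, so 12 + 3 = 15, with no allowance for dropout.

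- First doses: 31 × 0.0039 = 0.12 to 63 × 0.0140 = 0.88.
- Table 2 decisions: 31 × 15 × 0.0039 = 1.8 of 465, to 63 × 15 × 0.0140 = 13.2 of 945.

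I did not estimate a frequency for the 70 mg/dL case.

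**The case against.** The strongest reply is that the LY3209590 and hypoglycemia limits are not conversion errors. On unrounded values at 18.016, <3.9 mmol/L means below 3.9 × 18.016 = 70.3 mg/dL, which in whole numbers is exactly 70 or less. Likewise ≥7.8 means at least 140.5 mg/dL, which is exactly 141 or more. On a display that cuts off, both work as intended. The footnotes give the number of decimals but not the rounding rule. This stands, and it is why the 70 and 140 mg/dL mismatches are conditional. It does not rescue the pair of algorithms, because the degludec edge is wrong on a display that cuts off.

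The footnotes also show that one-decimal readings were considered, and each arm's bands around 7.8 leave no displayed value without a band. That explains the choice within LY3209590, but 7.8|7.9 avoids overlap equally well.

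Investigators may override the algorithm (Protocol 2.3.1), and LY3209590 is re-titrated weekly to Week 12. Both points limit the harm.

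A reader might go further and infer that the arms are biased against each other at 7.8. The documents do not support that. The algorithms differ by design in bands, units and dosing interval, and no effect on mean HbA1c can be derived. A reader might also want every mmol/L limit changed. With nearest rounding, 79 mg/dL shows as 4.4 and leaves the Table 2 reduction row, written as "<4.4 mmol/L or have any nocturnal hypoglycemia". But 80 mg/dL also shows as 4.4, so moving that row to ≤4.4 swaps one 1 mg/dL error for another and cuts the dose where the mg/dL rule gives a smaller cut or none. The 100 mg/dL target converts to 5.550–5.556, on the rounding edge, so any change there depends on the meter.

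**Conclusion.** The concern holds as a minor dosing-safety correction. Whatever the display rule, the two arms convert the same mg/dL edge differently and at least one is wrong. If the meter rounds to nearest, LY3209590 gets the higher band at 140 mg/dL, and the <3.9 limit lets a 70 mg/dL reading through in both arms.

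The windows are about 1 mg/dL wide. Under the assumed inputs, fewer than one first dose and about 2 to 13 Table 2 decisions would change at 140 mg/dL. The share of mmol/L users is not in the documents, so these counts only indicate scale.

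Three wider readings are not supported:

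- No effect on the primary HbA1c comparison is shown.
- Protocol 9.4.2.4 compares prescribed doses with the dose the investigator calculated, so no effect on adherence counts is shown.
- SAP 5.10.3.2 defines Level 1 hypoglycemia as below 70 mg/dL, so a reading of exactly 70 is not an analysed event in any case.

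**What to change.** First confirm from the meter specification that the mmol/L display rounds to nearest. If it does:

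1. In LY3209590 Table 1 use ≤7.8, and in Table 2 use 5.6–7.8. Start the next band at 7.9–10.0 in both, as for degludec.
2. Change <3.9 to ≤3.9 mmol/L in the hold and dose-decrease rules: Protocol 10.8.1 general considerations, Table 2 footnote d, and 10.8.2. For consistency, do the same in 6.1.2.2 and 8.3.7.1.

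If the meter cuts off instead, the LY3209590 bands and <3.9 are already right, and only the degludec edge is out (7.7|7.8 would match). Leave the 4.4 and 5.6 limits and the SAP event definitions as they are.

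The downside is that a displayed 7.8 or 3.9 then also treats 141 or 71 mg/dL as the lower value. That is the cautious side, at the price of an occasional smaller increase, or of 71 mg/dL counting as documented hypoglycemia. The change is to wording only, with no new procedures or data. It still alters dose rules, so it needs a protocol amendment with ethics approval (Protocol 10.1.1), matching patient instructions and a memo to sites.

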10.9. Appendix 9: Recommended Laboratory Testing for Hypersensitivity Events

Guidance for laboratory assessments for hypersensitivity events

Laboratory assessments should be performed if the participant experiences generalized urticaria or if anaphylaxis is suspected

- Collect sample after the participant has been stabilized, and within 1 to 2 hours of the event; however, samples may be obtained as late as 12 hours after the event as analytes can remain altered for an extended period of time. Record the time at which the sample was collected.
- Obtain a follow-up sample at the next regularly scheduled visit or after 4 weeks, whichever is later.

Table 4. Clinical Lab Tests for Hypersensitivity Events

The table content is completely redacted with a large black box. The letters 'CCI' are visible in red at the top left of the redacted area.

10.10. Appendix 10: Changes to Study Procedures due to the COVID-19 Pandemic or Natural Disasters

Remote Visits during the Study

If COVID-19 or natural disaster-related travel or shelter-in place restrictions are requested by local/regional authorities or for other reasons related to the pandemic or natural disasters which make it impossible for the participant to travel to the study site for the mandatory titration visits, mitigations are required to ensure safe and timely dosing of study participants.

The study site must receive prior approval by Lilly for either site mobile visits performed by trained site personnel or visits performed by a qualified home nursing service provider organized by the sponsor, with video-conferencing ability, to exceptionally replace the on-site visits.

Protocol procedures, including blood draws, data-downloads, participant (re-) education, study drug dose selection and study drug dosing may be performed at the participants' home by qualified personnel until travel or other restrictions are lifted. Collection of ECGs is optional during mobile visits

The allowed visit windows can be extended based on advice from Lilly Medical in this exceptional case to allow more flexibility in performing the home visits.

Early Discontinuation Procedures

If a participant is quarantined or contracts COVID-19 or is unable to attend the visit for other reasons during the course of the study and therefore mobile visits cannot be organized, study treatment must be discontinued early and dosing decisions for the alternative treatment are exceptionally allowed to be performed by telephone.

After termination of study treatment LY3209590 should be replaced by a non-insulin secretagogue and not by an insulin treatment to prevent hypoglycemia in this remote setting. The recommended alternative treatments are DPPIV inhibitors, SGLT2 inhibitors or GLP1 agonists. The alternative treatment should be started at the lowest recommended dose as soon as the participant's median fasting glucose rises above 140mg/dl during any 7-day period after the end of study treatment.

If the investigator sees an indication for treatment with another insulin product, a decision should be discussed with Lilly Medical.

Participants treated with insulin degludec can continue this treatment at the discretion of the investigator.

If remote or telephone visits are impossible and prohibit review of glycemic control, the participant must be hospitalized for a safe transition to an alternative antidiabetic treatment.

Participants will continue to enter their blood glucose- and hypoglycemia- information into their electronic diaries during the follow-up period to give the investigative site continued remote access to these data.

Study supplies for blood glucose monitoring as well as alternative treatments will be provided to the participant until the end of the safety follow-up period (6 weeks after the last dose of LY3209590 or 5 weeks after the last dose of insulin degludec). If circumstances permit, efforts may be made to obtain an immunogenicity blood sample after this follow-up. After the end of

the safety follow-up period, study supplies have to be returned or disposed as directed by the sponsor.

Replacement of study participants

The dropout rate will be monitored regularly during the study. If the dropout rate is over 15% prior to completion of 12 weeks of treatment, additional participants may be enrolled to ensure approximately 200 participants complete 12 weeks of treatment.

Documentation

The sites must identify and document the details of how all participants and visits were affected by the COVID-19 pandemic restrictions.

